1.0 Research Design

1.1 Purpose/Specific Aims

A. Objectives

This study will examine the feasibility, acceptability, and utility of neuroimaging technique to evaluate pre-exposure prophylaxis (PrEP) promotion messages for men who have sex with men (MSM) at risk of HIV in Baltimore, MD. The **specific aim** is:

Evaluate the effectiveness of PrEP promotion messages developed via a crowdsourcing open contest¹ by assessing neural bases of persuasion.

B. Hypotheses / Research Question(s)

This is an experimental study using neuroimaging technique to assess the persuasiveness of messages developed by a crowdsourcing open contest approach the study team conducted previously.

We hypothesize that, compared with participants viewing messages developed by a social marketing approach:

- H1. Participants viewing top messages developed via open contests will show higher brain activation in the Medial Prefrontal Cortex (MPFC) regions.
- H2. A greater proportion of participants viewing top messages developed via open contests will report increased willingness and behavioral intention to take PrEP.
- H3. A greater proportion of participants viewing top messages developed via open contests will report taking PrEP action and initiation during 30-day follow up.
- H4. Brain activation in the MPFC regions is significantly more correlated with PrEP action and initiation than self-reported message effectiveness.

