- All participants will complete a 30-day follow up survey by phone call or online to assess any behavioral change.

B. Data Points

- 1) Baseline: survey
- 2) In-person visit: neuroactivity and survey
- 3) 30-day follow up: online or phone survey

C. Study Duration

2 months

D. Endpoints

N/A

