1.6 Study Variables

A. Independent Variables, Interventions, or Predictor Variables

Intervention: top three messages developed by an open contest implemented in Baltimore¹.

B. Dependent Variables or Outcome Measures

Brain activity: fNIRS detects the ratio of oxygenated (O₂HB) to deoxygenated (HHB) hemoglobin based on their optical properties, with higher ratios indicating greater neural activity. Neural tissues are relatively transparent to light in the near infrared range between 700-1000 nm, and O₂HB and HHB reflect distinct wavelengths in this range. By modulating light at different wavelengths, emitting the light on the skin-exposed areas of the cranium, and detecting that light, fNIRS measures the blood oxygenation level dependent signal (BOLD) like fMRI. Because the photons reflected from neural tissue follow a reliable 'banana-shaped' path, photodetectors can be used to measure this on the scalp. By measuring the amount of absorbed light directed at the neural tissue, we can measure the amount of O₂HB and HHB present in a region of the brain at a given time and draw inferences about the level of neural activity.

PrEP-related beliefs, willingness, behavioral intention, and behavior:

All questions will be asked to participants at baseline (only to individuals aware of PrEP), at the in-person visit after reviewing all messages, and at the 30-day follow up, except questions on PrEP action and initiation, which will only be asked at the 30-day follow up.

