1.9 Data Collection

A. Primary Data Collection

▪ **Location:**

Baseline survey: in-person data collection in a private office

Neuroimaging data and post-messaging survey: in-person data collection at the private office in a community partner/community-based organization.

30-day follow up survey: online or over the phone

• **Process of Data Collection:**

Once an individual is screened eligible, he will provide an informed consent and complete a baseline survey. An in-person visit will be scheduled, roughly a week after completing the baseline survey. During the in-person visit, participants in each group will view multiple messages on a computer screen while brain activity is recorded. After completing all messages, participants will answer questions on perceived effectiveness of the messages, self-efficacy, and willingness and behavioral intention to use PrEP. Semi-structured questions on the acceptability of fNIRS will also be asked. All participants will complete a 30-day follow up by phone call or online to assess any behavioral change.

▪ **Timing and Frequency:**

Baseline survey, in-person visit/one week after completing the baseline survey, 30-day follow up

▪ **Procedures for Audio/Visual Recording:**

N/A.

▪ **Study Instruments:**

PrEP-related beliefs, willingness, behavioral intention, and behavior:

All questions will be asked to participants at baseline (only to individuals aware of PrEP), at the 2nd visit after reviewing all messages, and at the 30-day follow up, except questions on PrEP action and initiation, which will only be asked at the 30-day follow up.

Self-efficacy: Participants will be asked, on a 4-point Likert scale ranging from strongly disagree to strongly agree, to rate their agreement with the statement “I feel confident I could take PrEP as prescribed.”

Willingness: Participants will be asked, “Suppose that PrEP is at least 90% effective in preventing HIV when taken daily. How likely would you be to take PrEP if it were available for free?” with responses ranging from “I would definitely take it” to “I would definitely not take it.”⁶⁰

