Behavioral Intention: We will assess behavioral intentions to actually begin PrEP based on a real-world situation. To do this, participants will be asked, “PrEP is currently available with a prescription from your doctor and research has shown that a majority of insurance companies cover most or all of the costs of PrEP. Do you plan to begin PrEP?” Response options range from “Yes, I will definitely begin taking PrEP” to “No, I definitely will not begin taking PrEP.”

PrEP action and initiation: Items include “Have you spoken with a provider about PrEP during the past 30 days?” and “Have you started taking PrEP during the past 30 days?”

Message-related measures:

All questions will be asked after participants finish reviewing all messages during the in-person visit.

Perceived effectiveness: Participants will be asked, on a 4-point Likert scale ranging from strongly disagree to strongly agree, to rate their agreement that the message is believable, new, unconvincing, important to them, helps them feel confident about using PrEP, would help their friends use PrEP, put thoughts in their mind about using PrEP.

Baseline survey

Socioeconomic status: We will collect data on age, highest level of education attained, housing, employment history, health insurance status, access to health care, sources and amount of personal and household income,

Sexual identity: We will use a question from our previous study which asks participants to choose from heterosexual/straight, bisexual, homosexual/gay/same-gender loving, or not sure/questioning.

Sexual history: number of sex partners, sex of the partners, condom use in the past 90 days

Social media use: Types of social media sites used for socializing, seeking sex partners, and seeking health-related information.

HIV testing history

- **Ethnographic Studies, Interviews, Or Observation:**

N/A

- **Subject Identifiers:**

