4.0 Subject Considerations

4.1 Subject Selection and Enrollment Considerations

A. Method to Identify Potential Subjects

Participants will be recruited from a range of settings, including venue based outreach at community partner sites (CBOs, health clinics), street outreach, printed and online advertisements (CBO websites or Facebook pages), and word of mouth referral.

B. Recruitment Details

Recruitment staff will assess willingness of the establishment gatekeepers to permit recruitment activities. Recruitment of participants will be conducted by research staff who will receive extensive training in ethical guidelines regarding professional conduct and in how to approach and engage potential study participants. Staff will be asked to sign a pledge to protect respondent privacy and confidentiality. Recruitment staff will have a cellular phone to contact the study PI and/or security in the event that they are concerned about their safety. Each person approached will be given a project recruitment flyer that provides basic information regarding the study. Potential participants will be given information about the nature of the study, the time involved, and informed that they will be financially reimbursed for their time. In order to reduce potential embarrassment or inadvertent disclosure of HIV or sexual behaviors the script will include the comment, "If this doesn't apply to you, please give it to someone you know."

C. Subject Screening

Participants will provide verbal consent to be screened for the study. Eligible participants will be asked to provide written consent, complete a baseline survey and scheduled for the baseline visit.

- Inclusion Criteria**

Key inclusion criteria in this study are 1) 18 years and older; 2) biological male sex at birth; 3) sexually active with men in the past 6 months; 4) never taken PrEP; 5) HIV negative; 6) reside in Baltimore City or surrounding counties; and 7) meet one of the criteria for being an appropriate PrEP candidate¹: a) in a relationship with a partner not known to be HIV-negative, b) were in a nonmonogamous relationship, c) had any condomless anal sex with a casual male partner regardless of status in the prior 6 months, or d) had a positive STI diagnosis within the prior 6 months.

- Exclusion Criteria**

N/A

D. Privacy Protections

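### The H3 items look back 30 days from the survey date, not from the message visit, so early or late surveys can misclassify PrEP action and initiation

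*Combined protocol and SAP*

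**What the plan says.** - **Hypothesis.** Section 1.1, H3: a larger share of participants who view the open-contest messages "will report taking PrEP action and initiation during 30-day follow up". H4 relates brain activation to the same outcome.
- **Items.** Section 1.9 lists "Have you spoken with a provider about PrEP during the past 30 days" and "Have you started taking PrEP during the past 30 days". Neither refers to the message visit, and no event date is listed.
- **When asked.** Section 1.6 has the PrEP questions asked at several time points, "except questions on PrEP action and initiation, which will only be asked at the 30-day follow up".
- **Exposure.** Messages are shown at the second visit. Section 1.9: "An in-person visit will be scheduled, roughly a week after completing the baseline survey".
- **Schedule.** The timing entry in section 1.9 reads "Baseline survey, in-person visit/one week after completing the baseline survey, 30-day follow up". Section 1.3 adds: "All participants will complete a 30-day follow up survey by phone call or online to assess any behavioral change". Neither gives a starting day or an allowed range of days.
- **Eligibility.** Section 4.1 requires "4) never taken PrEP". It sets no limit on earlier conversations with a provider.

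**The concern.** The period of interest for H3 starts when the messages are viewed. The recall period starts 30 days before the survey is answered. The two coincide only if the survey is answered exactly 30 days after viewing, and nothing in the documents requires that.

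An early survey counts days before any message was seen. The provider-talk item is the more exposed: nothing limits earlier talks, whereas the eligibility criterion confines a pre-message PrEP start to the gap of about a week between baseline and the visit. A late survey has the opposite fault. A participant who starts PrEP on day 2 and answers truthfully on day 35 is scored as a non-starter. Without event dates, neither error can be corrected for the individual participant.

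Misclassification of this outcome affects both H3 and H4. Section 1.5 also intends the effect sizes from this study to inform the design of a larger trial, so an attenuated estimate would be carried forward.

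**Working it through.** The documents give no event rate, effect size or power for H3, so there is no stated figure to reproduce. All rates below are assumptions.

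**1. Window arithmetic.** Let T be the days from message viewing to the survey.
- Pre-message days counted = max(0, 30 − T).
- Post-message days missed = max(0, T − 30).
- T = 30 gives 0 and 0. T = 23 gives 7 pre-message days, 7/30 = 23% of the window. T = 40 gives 10 missed days.

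T = 23 is a survey seven days early. It is also where the survey would fall if the clock ran from the baseline survey, given the gap of about a week.

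**2. Assumptions for illustration.** True 30-day rates of 10% (social marketing) and 30% (open contest), a constant daily rate, 30 per arm (half of the 60 in section 1.3), two-sided alpha 0.05. The pre-message background is 5% or 10% per 30 days in both arms. On schedule the difference is 20 points. Power is 49% (normal approximation) or 37% (Fisher's exact test).

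**3. Survey seven days early (T = 23).**
- Background 10%: social marketing stays at 10.0%. Open contest: 1 − 0.90^(7/30) × 0.70^(23/30) = 25.8%. Difference 15.8 points.
- Background 5%: social marketing 1 − 0.95^(7/30) × 0.90^(23/30) = 8.9%. Open contest 1 − 0.95^(7/30) × 0.70^(23/30) = 24.8%. Difference 16.0 points.
- Power falls to 35–38% (Fisher 24–25%).

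Most of this loss comes from the shorter follow-up. With pre-message events removed altogether, the day-23 difference is 0.90^(23/30) − 0.70^(23/30) = 0.922 − 0.761 = 16.2 points. Rewording the items would not restore the 20 points; a survey window that opens on day 30 would.

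**4. Late survey, provider item, constant rate.** At T = 40 the last 30 days all follow exposure, so the rates remain 10% v 30%. Nothing is lost in this model.

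**5. Late survey, initiation item, constant rate.** A start happens once, so only starts between days 10 and 40 count.
- Social marketing: 0.90^(10/30) × 0.10 = 9.7%.
- Open contest: 0.70^(10/30) × 0.30 = 26.6%.
- Difference: 17.0 points.

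**6. Late survey, severe case.** Suppose the whole excess falls in the first 10 days after viewing. The excess cumulative hazard is ln(0.90/0.70) = 0.251.
- T = 33 keeps 7/10 of it: 1 − 0.90 × exp(−0.176) = 24.5%. Difference 14.5 points, power about 32%.
- T = 37 keeps 3/10: 1 − 0.90 × exp(−0.075) = 16.5%. Difference 6.5 points, power about 11%.

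The documents do not say whether an effect of the messages would be front-loaded.

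**The case against.** The strongest reply is that the wording suits the planned schedule. Sections 1.3 and 1.9 list the steps in order: baseline, message visit, post-message questions, then the 30-day survey. On that order the 30 days run from the message visit, and a survey on day 30 has no mismatch. This stands. Only departures from schedule matter, and the documents do not show how large they would be.

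A reader might infer more, in four ways:

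- **That 23% of the recall window precedes exposure by design.** This needs a clock that starts at baseline. Some wording leaves room for it: section 4.1 calls the appointment after the baseline survey a baseline visit, and section 6.1 measures change in willingness and intention from baseline. It is still the less natural reading.
- **That a survey on day 40 or 45 loses a quarter or a third of the effect.** (40 − 30)/40 = 25% and (45 − 30)/45 = 33% are shares of calendar days. Under a constant rate the provider item loses nothing, and initiation loses about 3 points at day 40.
- **That the bias must be towards zero.** This assumes similar survey timing in both arms. With similar timing, randomisation balances pre-message events in expectation, so they do not create a false difference. With different timing, the bias can go either way.
- **That nothing could be recovered afterwards.** Section 4.6 records payment dates by study ID, so the interval from visit to survey should be largely recoverable for a sensitivity analysis. Section 1.9 introduces the items as examples, so the full questionnaire may hold more. Event dates, however, are not among the listed items.

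The preliminary purpose in section 1.5 lowers the weight of the power figures. It does not remove the case for measuring the outcome over the intended period.

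**Conclusion.** The point holds as a measurement weakness that depends on survey timing. The items are not tied to message viewing, the start of the 30 days is not stated, and no survey window is set. The documents do not show that dilution will occur: with a survey exactly 30 days after viewing there is none.

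Away from day 30, the H3 difference can be attenuated and error added to H4 if timing is similar in both arms; otherwise the direction is open. Under assumed rates of 10% v 30% and a constant daily rate, the difference falls from 20 to about 16 points for a survey seven days early, and to about 17 points for initiation at day 40. Larger losses require the effect to be concentrated in the first days. The true size is unknown, because neither event rates nor the spread of survey dates is given. Weight: minor to moderate, and worth acting on because the change costs little.

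**What to change.** 1. State in section 1.9 that the 30 days run from message viewing, and set a survey window that opens on day 30 and has a stated closing day.
2. Reword both items to *Since your study visit on [date], have you ...?*
3. Record the date of the first provider talk and of the PrEP start.
4. Count events from after viewing on the visit day through day 30. Starting the count on the next day would lose a provider talk held later on the visit day.

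A baseline provider-talk item is optional at most. It would cover the time before baseline and not the week between baseline and the visit, and asking it could prompt the behaviour being measured.

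Cost: two reworded items, two date fields and a short addition to section 1.9. The follow-up survey becomes slightly longer, and recalled dates will carry some error.

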1.10 Timetable/Schedule of Events

Study Activity							
	0	2	4	6	8	10	12
Training and IRB approval							
Recruit participants and collect baseline survey							
Conduct neuro-influence experiment using fNIRS							
Collect follow up survey							
Analyze data, write manuscripts and develop dissemination report							
Develop applications for future work							

2.2 Research Staff Training

All research staff who will receive extensive training in ethical guidelines regarding professional conduct and in how to approach and engage potential study participants.

While there is currently no formal training or certification required for use of an fNIRS device, attending a training workshop such as those offered yearly by BIOPAC Systems Inc., a company that sells fNIRS equipment in the United States, and the Athinoula A. Martinos Medical Center in Massachusetts that offers 3 day workshops, will be required for research staff who will operate fNIRS. They will also be supervised by study consultant [name].

2.3 Other Resources

JOY Baltimore is a LGBTQ-serving organization in Baltimore. JOY Baltimore provides access to emergency and permanent housing, medical and dental services, community services vital records and MD State ID. Since 2017, [name] has collaborated with JOY Baltimore on an NIH-funded project (R34MH116725) to develop pre-exposure prophylaxis (PrEP) promotion messages for Black young adults in Baltimore. JOY Baltimore will offer private office for [name] with a locked cabinet to store project-related documents and a private space for participants enrollment and data collection.

3.0 Multi-Center Research

N/A

4.0 Subject Considerations

4.1 Subject Selection and Enrollment Considerations

A. Method to Identify Potential Subjects

Participants will be recruited from a range of settings, including venue based outreach at community partner sites (CBOs, health clinics), street outreach, printed and online advertisements (CBO websites or Facebook pages), and word of mouth referral.

B. Recruitment Details

Recruitment staff will assess willingness of the establishment gatekeepers to permit recruitment activities. Recruitment of participants will be conducted by research staff who will receive extensive training in ethical guidelines regarding professional conduct and in how to approach and engage potential study participants. Staff will be asked to sign a pledge to protect respondent privacy and confidentiality. Recruitment staff will have a cellular phone to contact the study PI and/or security in the event that they are concerned about their safety. Each person approached will be given a project recruitment flyer that provides basic information regarding the study. Potential participants will be given information about the nature of the study, the time involved, and informed that they will be financially reimbursed for their time. In order to reduce potential embarrassment or inadvertent disclosure of HIV or sexual behaviors the script will include the comment, "If this doesn't apply to you, please give it to someone you know."

C. Subject Screening

Participants will provide verbal consent to be screened for the study. Eligible participants will be asked to provide written consent, complete a baseline survey and scheduled for the baseline visit.

- Inclusion Criteria**

Key inclusion criteria in this study are 1) 18 years and older; 2) biological male sex at birth; 3) sexually active with men in the past 6 months; 4) never taken PrEP; 5) HIV negative; 6) reside in Baltimore City or surrounding counties; and 7) meet one of the criteria for being an appropriate PrEP candidate¹: a) in a relationship with a partner not known to be HIV-negative, b) were in a nonmonogamous relationship, c) had any condomless anal sex with a casual male partner regardless of status in the prior 6 months, or d) had a positive STI diagnosis within the prior 6 months.

- Exclusion Criteria**

N/A

D. Privacy Protections

The protocol recognizes that the major danger of a breach of confidentiality lies with the research staff who know both the identity of the participants and the data furnished. It is recognized that there is no absolutely certain way to prevent breaches of confidentiality by interviewers, but the risk of breach will be minimized through careful selection and training of the interviewers. Any new staff will be carefully selected based on qualifications and prior experience, with all of the identified research staff and interviewers already known to the PI. All project staff members are required to complete the Protection of Human Subjects Computer-based Training and Education program. All project staff will sign a pledge of confidentiality. Utmost care will be taken when contacting participants about enrollment and participation. Study staff will only talk to the participant directly unless the participant has authorized staff to leave a message or have contact with others pursuant to follow up visits. Data can be readily downloaded and converted to the format of commercially available statistical software. Participants provide contact information (email address or phone numbers) which will be kept in secured Participation Database. All personal information about each participant is kept separate from the participant's ID number. We maintain a master list that links code number and identified information. The linkage between code number and identifiable information will be encrypted and saved on a password-protected server. The master list must be retained in order to plan subsequent stages of follow up, but it will be destroyed at the completion of the study.

Questions in the surveys will include sensitive information, such as sexual behaviors. This information could be potentially damaging to the subjects. The information will be obtained by a trained interviewer supervised by staff experienced in carrying out this activity and maintaining confidentiality in the various phases of the study. This study will be funded by NIH, and study data will be protected from the Attorney General of the United States under the Comprehensive Drug Abuse Prevention and Control Act of 1970 (i.e., Certificate of Confidentiality).

UPLOAD to e-IRB Section 11.0 Recruitment Materials – *all* recruitment materials, such as: in-person or telephone scripts, emails, flyers, posters, social media posts, and radio or television advertisement scripts, etc. that will be used to recruit individuals to the study.

